6.2 Bioanalytical Method

6.2.1 Repaglinide

Plasma concentrations of repaglinide will be determined using a liquid chromatography-tandem mass spectrometry (LC-MS/MS) method validated with respect to accuracy, precision, linearity, sensitivity, and specificity at Alturas Analytics, Inc. (Moscow, Idaho, USA). The analytical range (lower limit of quantitation [LLOQ] – upper limit of quantitation [ULOQ]) for repaglinide in plasma is 0.02 – 20 ng/mL.

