6.2.2 LOXO-292

Plasma concentrations of LOXO-292 will be determined using LC-MS/MS method validated with respect to accuracy, precision, linearity, sensitivity, and specificity at

Alturas Analytics, Inc. (Moscow, Idaho, USA). The analytical range (LLOQ – ULOQ) for LOXO-292 in plasma is 1 – 1000 ng/mL. Samples that contain concentrations greater than 1000 ng/mL may be diluted up to 51-fold, if necessary, to be within the quantification range.

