6.6 Data Summarization and Presentation

All repaglinide and LOXO-292 PK concentrations and PK parameters descriptive statistics will be generated using SAS® Version 9.3 or higher.

The plasma concentrations of repaglinide will be listed and summarized by treatment and time point for all subjects in the PK Population. The plasma concentrations of LOXO-292 will be listed and summarized by Study Day and time point for all subjects in the PK Population. Plasma concentrations of repaglinide and LOXO-292 will be presented with the same level of precision as received from the bioanalytical

laboratory. Summary statistics, including sample size (n), arithmetic mean (Mean), standard deviation (SD), coefficient of variation (CV%), standard error of the mean (SEM), minimum, median, and maximum will be calculated for all nominal concentration time points. Excluded subjects will be included in the concentration listings, but will be excluded from the summary statistics and noted as such in the tables. All BLQ values will be presented as “BLQ” in the concentration listings and footnoted accordingly.

Mean and individual concentration-time profiles will be presented on linear and semi-log scales. Linear mean plots will be presented with and without SD.

Plasma repaglinide PK parameters will be listed and summarized by treatment for all subjects in the PK Population. Plasma LOXO-292 PK parameters will be listed and summarized by Study Day for all subjects in the PK Population. PK parameters will be reported to 3 significant figures for individual parameters, with the exception of Tmax and t½, which will be presented with 2 decimal places. Summary statistics (n, Mean, SD, CV%, SEM, minimum, median, maximum, geometric mean [Geom Mean] and geometric CV% [Geom CV%]) will be calculated for plasma repaglinide and LOXO-292 PK parameters. Excluded subjects will be listed in the PK parameter tables, but will be excluded from the summary statistics and noted as such in the tables.

The level of precision for each concentration and PK parameter statistic will be presented as follows:

- minimum/maximum in same precision as in bioanalytical data and parameter output,
- mean/median/Geom Mean in one more level of precision than minimum/maximum,
- SD/SEM in one more level of precision than mean/median/Geom Mean,
- n will be presented as an integer, and
- CV%/ Geom CV% will be presented to the nearest tenth.

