10.2 Figures Shells

In-text Figures 11-1 through 11-3 and Figures 14.2.1.2.2, 14.2.2.2.2, and 14.2.2.2.5 will be in the following format:

Figure 11-1 Arithmetic Mean Plasma Repaglinide Concentration-Time Profiles Following Administration of a Single Dose of 0.5 mg Repaglinide Alone (Treatment A) and Coadministered with Multiple Twice Daily Doses of 160 mg LOXO-292 (Treatment B) (Pharmacokinetic Population)

Program: /CAXXXXX/sas_prg/pksas/adam_meangraph.sas DDMMYYYY HH:MM
Program: /CAXXXXX/sas_prg/pksas/meangraph.sas DDMMYYYY HH:MM

[figure not shown]
Notes for Generating the Actual Mean Figure:

- Figures 11-1 and 14.2.1.2.2:
 - Legend will be:
 - Treatment A: 0.5 mg Repaglinide Alone
 - Treatment B: 0.5 mg Repaglinide + Multiple BID 160 mg LOXO-292
 - Y-axis label will be “Plasma Repaglinide Concentration (ng/mL)”
 - X-axis label will be “Hours Postdose (hr) from Repaglinide Dose”
 - Add in footnote: LLOQ value for repaglinide is 0.02 ng/mL
- Figures 11-2 and 14.2.2.2.2:
 - Legend will be:
 - 160 mg LOXO-292 on Day 1
 - Multiple BID Doses of 160 mg LOXO-292 + 0.5 mg Repaglinide on Day 10
 - Y-axis label will be “Plasma LOXO-292 Concentration (ng/mL)”
 - X-axis label will be “Hours Postdose (hr) from LOXO-292 Morning Dose”
 - Add in footnote: LLOQ value for LOXO-292 is 1.00 ng/mL.
- Figure 11-3 and Figure 14.2.2.2.5:
 - Legend will be:
 - Multiple BID Doses of 160 mg LOXO-292
 - Y-axis label will be “Plasma LOXO-292 Concentration (ng/mL)”
 - X-axis label will be “LOXO-292 Ctrough Day”
 - Add footnote: Ctrough Days 1 through 9 are the predose samples on dosing Days 2 through 10.

Program: /CAXXXX/sas_prg/pksas/meangraph.sas DDMMYYYY HH:MM
Program: /CAXXXX/sas_prg/pksas/adam_meangraph.sas DDMMYYYY HH:MM

Figures 14.2.1.2.1, 14.2.2.2.1, and 14.2.2.2.4 will be in the following format:

Figure 14.2.1.2.1 Mean (SD) Plasma Repaglinide Concentration-Time Profiles Following Administration of a Single Dose of 0.5 mg Repaglinide Alone (Treatment A) and Coadministered with Multiple Twice Daily Doses of 160 mg LOXO-292 (Treatment B) (Linear Scale) (Pharmacokinetic Population)

[figure not shown]
Notes for Generating the Actual Mean Figure:

- Figure 14.2.1.2.1:
 - Legend will be:
 - Treatment A: 0.5 mg Repaglinide Alone
 - Treatment B: 0.5 mg Repaglinide + Multiple BID 160 mg LOXO-292
 - Y-axis label will be “Plasma Repaglinide Concentration (ng/mL)”
 - X-axis label will be “Hours Postdose (hr) from Repaglinide Dose”

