10.3 Post-text Table Shells

Table 14.1.1.1 Summary of Disposition (Safety Population)

Page X of X

Disposition	Treatment		
	A	B	Overall
Enrolled	XX	XX	XX
Completed	XX	XX	XX
Discontinued Early	XX	XX	XX
Reason 1	XX	XX	XX
Reason 2	XX	XX	XX
Reason 3	XX	XX	XX
etc.			

Note: Treatment A: A single dose of 0.5 mg repaglinide administered at Hour 0 on Day 1

Treatment B: Multiple doses of 160 mg LOXO-292 (2 x 80 mg capsules) administered BID, approximately every 12 hours, for 10 consecutive days with 0.5 mg repaglinide (coadministered on the morning of Day 10)

Program: /CAXXXX/sas_prg/stsas/tbl_PROGRAMNAME.sas DDMMYYYY HH:MM

Table 14.1.1.2 Disposition of Subjects (Safety Population)

Subject Number	Treatment Sequence	Dosed Period		Completed Period		Study Completion	
		1	2	1	2	Status	Date
XXX-XXX	AB	Yes	Yes	Yes	Yes	Completed Study	DDMMYYYY
XXX-XXX	AB	Yes	Yes	Yes	No	Terminated Study Prematurely	DDMMYYYY

Note: Treatment A: A single dose of 0.5 mg repaglinide administered at Hour 0 on Day 1
Treatment B: Multiple doses of 160 mg LOXO-292 (2 x 80 mg capsules) administered BID, approximately every 12 hours, for 10 consecutive days with 0.5 mg repaglinide (coadministered on the morning of Day 10)

Program: /CAXXXX/sas_prg/stsas/tab_PROGRAMNAME.sas DDMMYYYY HH:MM

Table 14.1.1.3 Demographic Summary (Safety Population)

Trait		Study Overall
Sex	Male	X (XX%)
	Female	X (XX%)
Race	Asian	X (XX%)
	Black or African American	X (XX%)
	White	X (XX%)
Ethnicity	Hispanic or Latino	X (XX%)
	Not Hispanic or Latino	X (XX%)
Age* (yr)	n	XX
	Mean	XX.X
	SD	X.XX
	Minimum	XX
	Median	XX.X
	Maximum	XX
Height (cm)	n	XX
	Mean	XX.X
	SD	X.XX
	Minimum	XX
	Median	XX.X
	Maximum	XX

Programmer Note: Also include weight (kg) and BMI (kg/m²)

Note: * Age is calculated from the date of first dosing.

BMI = Body mass index

Program: /CAXXXX/sas_prg/stsas/tab_PROGRAMNAME.sas DDMMMYYYY HH:MM

Tables 14.2.1.1.1, 14.2.1.1.2, and 14.2.2.1.1 through 14.2.2.1.3 will be in the following format:

Table 14.2.1.1.1 Plasma Repaglinide Concentrations (ng/mL) Following Administration of a Single Dose of 0.5 mg Repaglinide Alone (Treatment A)
(Pharmacokinetic Population)

Subject Number	Treatment Sequence	Study Period	Predose	Sample Times (hr)								-
				XX	XX	XX	XX	XX	XX	XX	XX	
XXX-XXX	XXX	X	BLQ	XX	XX	XX	XX	XX	XX	XX	XX	XX
XXX-XXX	XXX	X	BLQ	XX	XX	XX	XX	XX	XX	XX	XX	XX
XXX-XXX	XXX	X	BLQ	XX	XX	XX	XX	XX	XX	XX	XX	XX
n				XX	XX	XX	XX	XX	XX	XX	XX	XX
Mean				XX.X	XX.X	XX.X	XX.X	XX.X	XX.X	XX.X	XX.X	XX.X

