SD				XX.XX	XX.XX	XX.XX	XX.XX	XX.XX	XX.XX	XX.XX	XX.XX	XX.XX
CV%				.	XX.X							
SEM				XX.XX	XX.XX	XX.XX	XX.XX	XX.XX	XX.XX	XX.XX	XX.XX	XX.XX
Minimum				XX	XX	XX	XX	XX	XX	XX	XX	XX
Median				XX.X	XX.X	XX.X	XX.X	XX.X	XX.X	XX.X	XX.X	XX.X
Maximum				XX	XX	XX	XX	XX	XX	XX	XX	XX

For the calculation of summary statistics, values that are below the limit of quantitation (BLQ) of 1 ng/mL are treated as 0 before the first quantifiable concentration and as missing elsewhere.

. = Value missing or not reportable.

Notes for Generating the Actual Table:

Presentation of Data:

- Present the subject number in the following format: XXX-XXX
- Concentrations will be presented to same precision as in the bioanalytical data.
- Summary statistics presentation with respect to the precision of the bioanalytical data: n = integer; Mean and Median +1; SD and SEM +2, Min and Max +0, CV% to 1 decimal

Programmer Note:

- PK Time points are:
 - Tables 14.2.1.1.1 and 14.2.1.1.2: CCI
 - Table 14.2.2.1.1: CCI
 - Table 14.2.2.1.2: CCI
 - Table 14.2.2.1.3: CCI

Per study design needs, the following changes are made to this table relative to Celerion standard:

1. Please remove the “Treatment Sequence” column

Program: /CAXXXX/sas_prg/pksas/pk-conc-tables.sas	DDMMYYYY HH:MM
Program: /CAXXXX/sas_prg/pksas/pk-conc-tables-sig.sas	DDMMYYYY HH:MM
Program: /CAXXXX/sas_prg/pksas/adam_conc.sas	DDMMYYYY HH:MM

Tables 14.2.1.1.3, 14.2.1.1.4, and 14.2.2.1.4 and 14.2.2.1.5 will be in the following format:

Table 14.2.1.1.3 Plasma Repaglinide Pharmacokinetic Parameters Following Administration of a Single Dose of 0.5 mg Repaglinide Alone (Treatment A)
 (Pharmacokinetic Population)

Subject Number	Treatment Sequence	Study Period	Parameters					
			param1 (units)	param2 (units)	param3 (units)	param4 (units)	param5 (units)	param6 (units)
XXX-XXX	XXX	X	XXX	X.XX	XXX	XXX	XX.X	X.XXX
XXX-XXX	XXX	X	XX.X	X.XX	XXX	XXX	XX.X	X.XXX
XXX-XXX	XXX	X	XXX	X.XX	XXX	XXX	XX.X	X.XXX
XXX-XXX	XXX	X	XX.X	X.XX	XXX	XXX	XX.X	X.XXX
XXX-XXX	XXX	X	XX.X	X.XX	XXX	XXX	XX.X	X.XXX
XXX-XXX	XXX	X	XX.X	X.XX	XXX	XXX	XX.X	X.XXX
XXX-XXX	XXX	X	XXX	X.XX	XXX	XXX	XX.X	X.XXX
n			XX	XX	XX	XX	XX	XX
Mean			XXX.X	X.XXX	XXX.X	XXX.X	XX.XX	X.XXXX
SD			XX.XX	XX.XX	XX.XX	XX.XX	XX.XX	XX.XX
CV%			XX.X	XX.X	XX.X	XX.X	XX.X	XX.X
SEM			XX.XX	XX.XX	XX.XX	XX.XX	XX.XX	XX.XX
Minimum			XX.X	X.XX	XXX	XXX	XX.X	X.XXX
Median			XX.XX	X.XXX	XXX.X	XXX.X	XX.XX	X.XXXX
Maximum			XXX	X.XX	XXX	XXX	XX.X	X.XXX
Geom Mean			XXX.X	X.XXX	XXX.X	XXX.X	XX.XX	X.XXXX

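### The shell for the repaglinide concentration tables prints a BLQ limit of 1 ng/mL, which is the LOXO-292 LLOQ and 50 times the repaglinide LLOQ of 0.02 ng/mL

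*SAP*

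**What the plan says.** SAP 10.3 gives one layout for five concentration tables: "Tables 14.2.1.1.1, 14.2.1.1.2, and 14.2.2.1.1 through 14.2.2.1.3 will be in the following format". The first two are repaglinide tables and the other three are LOXO-292 tables. The shell is drawn under the title of Table 14.2.1.1.1, a repaglinide table. Its footnote on summary statistics reads "BLQ) of 1 ng/mL are treated as 0 before the first quantifiable concentration and as missing elsewhere".

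The assay limits are in SAP 6.2. The analytical range "for repaglinide in plasma is 0.02 – 20 ng/mL" (6.2.1), and that for "LOXO-292 in plasma is 1 – 1000 ng/mL" (6.2.2).

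The figure shells in SAP 10.2 are also shared between analytes, but there the footnote changes with the analyte: "Add in footnote: LLOQ value for repaglinide is 0.02 ng/mL" for repaglinide and "Add in footnote: LLOQ value for LOXO-292 is 1.00 ng/mL" for LOXO-292. The table shell has no such switch in its visible notes. They vary the sample times by table. Under the line "the following changes are made to this table relative to Celerion standard" they list a single item, removal of the treatment-sequence column.

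**The concern.** The stated limit is right for three of the five tables and wrong for two, including the one it is printed under. Repaglinide is the analyte of the primary objective.

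The footnote also does more than label the table. It is the only text in the supplied documents that says how BLQ values enter the concentration summaries:

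- SAP 6.5 gives a BLQ rule, but for the calculation of PK parameters.
- SAP 6.6 lists the summary statistics and says how BLQ values appear in the listings. It does not say how they are counted in the statistics.

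Two consequences are possible:

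- **At minimum**, a reader of the two repaglinide tables sees numeric values below 1 ng/mL above a footnote that declares such values unquantifiable.
- **If the footnote is programmed as written**, quantified repaglinide values from 0.02 to just under 1 ng/mL become zero on the way up and missing on the way down. The n, mean, SD and median at those time points change. The table means could then disagree with the mean plots, which SAP 6.1 bases on all concentration data apart from possible exclusions for sampling-time deviations.

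The direction of error is not fixed. Zeros pull a mean down, and dropping low late values pushes it up. The footnote does not say what happens to a profile that never reaches 1 ng/mL.

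**Working it through.** **Inputs**

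- Footnote limit: 1 ng/mL (SAP 10.3).
- Repaglinide assay range: 0.02 to 20 ng/mL (SAP 6.2.1; the LLOQ is repeated in the repaglinide figure shells of SAP 10.2).
- LOXO-292 assay range: 1 to 1000 ng/mL (SAP 6.2.2; the LLOQ is repeated in the LOXO-292 figure shells).
- Repaglinide half-life: about 1 h (Protocol 8.1.2).
- Repaglinide sampling window: 16 h postdose (SAP 3).

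**Comparison of limits**

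| Tables | Analyte | Footnote limit (ng/mL) | Assay LLOQ (ng/mL) | Ratio |
|---|---|---|---|---|
| 14.2.1.1.1, 14.2.1.1.2 | repaglinide | 1 | 0.02 | 1/0.02 = 50 |
| 14.2.2.1.1 to 14.2.2.1.3 | LOXO-292 | 1 | 1 | 1 |

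This comparison is enough to establish the point. The rest only shows how wide the mislabelled range is.

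**Share of the assay range (log scale)**

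- log2(1/0.02) = 5.64 half-lives.
- log2(20/0.02) = 9.97 half-lives.
- 5.64/9.97 = 0.566, or about 57% of the repaglinide assay range.

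**Time spent between 1 and 0.02 ng/mL on the decline**

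At a half-life of 1 h this is 5.64 h, and 5.64/16 = 35% of the sampling window.

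To place that stretch, assume log-linear decline from a peak at 1 h:

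- Cmax of 1 ng/mL: from 1.0 h to 1 + 5.64 = 6.6 h.
- Cmax of 20 ng/mL: from 1 + log2(20) = 5.3 h to 1 + 9.97 = 11.0 h.

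For any Cmax in that range the whole stretch falls inside 16 h. The documents give only the approximate 1 h half-life, so other values are assumptions:

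| Assumed half-life | Length of stretch | Share of 16 h | Latest end (Cmax 20 ng/mL) |
|---|---|---|---|
| 0.8 h | 4.5 h | 28% | 9.0 h |
| 1.0 h | 5.6 h | 35% | 11.0 h |
| 1.5 h | 8.5 h | 53% | 15.95 h |
| 2.0 h | 11.3 h | (runs past the window) | 20.9 h |

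The number of table values affected, and the size or direction of the error in any mean, cannot be derived. The sampling times are redacted, and the documents give no expected repaglinide concentrations.

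**The case against.** The strongest reply is that nobody chose to censor repaglinide at 1 ng/mL. Every other statement of the repaglinide limit is 0.02 ng/mL, and 1 ng/mL is correct for most of the tables that share the shell. SAP 10 says the shells convey general layout and may change. The body of the SAP points away from a literal reading: SAP 6.4 takes concentrations as measured by the methods in 6.2, and SAP 6.6 says "Plasma concentrations of repaglinide and LOXO-292 will be presented with the same level of precision as received from the bioanalytical" laboratory. A programmer would have to override numeric laboratory results to produce wrong statistics. This stands. It makes a carried-over footnote much the likelier explanation and keeps the severity low. It does not make the footnote correct, and no other text states the BLQ rule for these summaries.

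A second objection is that the first quantifiable concentration may mean the first at or above the assay LLOQ, not the first of at least 1 ng/mL. The text leaves this open. On that reading, though, a value of, say, 0.5 ng/mL is both quantifiable by the assay and BLQ by the footnote, so the contradiction remains.

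A third objection is that the half-life arithmetic describes a hypothetical curve. It omits the rising limb and any Cmax below 1 ng/mL. It also treats both periods alike, although inhibition of CYP2C8 by LOXO-292 could lengthen the half-life in Treatment B. The claim that the stretch lies wholly inside the window fails once the half-life exceeds 15/9.97, or about 1.5 h, for a Cmax of 20 ng/mL. This is fair: those figures illustrate width only, and the finding does not rest on them.

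**Conclusion.** The concern holds, as a minor point. The BLQ limit in the shared shell is wrong for Tables 14.2.1.1.1 and 14.2.1.1.2 by a factor of 50, and no visible note corrects it. That conclusion rests only on the two stated LLOQs and the footnote, with no modelling assumption. The redactions near this shell cover the sample times, not the limit.

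The reach is confined to descriptive concentration tables. The geometric mean ratios and 90% CIs for AUC0-t, AUC0-inf and Cmax follow the BLQ rule in SAP 6.5, which names no numeric limit, and Kel in Table 6.1 uses concentrations above the LLOQ. Neither depends on 1 ng/mL, so the primary comparison is unchanged.

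**What to change.** Make the footnote analyte-specific, in the way the figure shells already are: a limit of 0.02 ng/mL for Tables 14.2.1.1.1 and 14.2.1.1.2, and 1 ng/mL for Tables 14.2.2.1.1 to 14.2.2.1.3. The cost is one edited footnote. Data, sampling and the inferential analysis do not change.
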